14.1.1. Sample Size for Primary Efficacy Endpoint

The statistical hypotheses are:

$$H_0: \mu_d = \mu_p,$$
$$H_1: \mu_d \neq \mu_p,$$

where μ_d and μ_p are the mean change in log-transformed 24-hour UPE from baseline to 36 weeks for narsoplimab and placebo, respectively.

Based on IgAN patient registry data from University Hospital Leicester, UK, the log scale standard deviation for the change in UPE from baseline to 9 months in IgAN patients with ≥ 2 g/day is estimated to be 0.80. Hypothesizing a treatment effect on UPE of 35% (-0.393 on the log scale), a total N of 180 patients with a baseline UPE ≥ 2 g/day need to be randomized on a 1:1 basis to narsoplimab or placebo to provide 95% power to test the stated hypotheses, at the 2-sided 5% alpha level. Data from the preplanned blinded sample size reassessment for UPE at 9 months in the high-risk proteinuria population (baseline UPE ≥ 2 g/day) gave blinded logscale SD estimates of 0.63, hence the sample size of N = 180 is supported.

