### Tipping Point Multiple Imputation

The second approach analysis will be a tipping point analysis. This will assess the robustness of the primary endpoint analysis by determining the penalty that, when applied to narsoplimab patients with missing data, renders the primary endpoint p-value non-significant. This analysis requires that the data has a monotone missingness pattern, thus, and as necessary, a partial-imputation method using the MCMC method will be employed as described above for Jump to Placebo.

The penalty to render a non-significant primary endpoint p-value will be determined via search as follows. Let the log scale treatment effect estimate from the primary UPE endpoint analysis be denoted as  $\theta\theta\theta\theta\theta\theta$ , then the set of penalty values,  $\{\delta\delta\delta\delta\}$ , to be evaluated will be  $0.00 \cdot \theta\theta\theta\theta\theta\theta, 0.05 \cdot \theta\theta\theta\theta\theta\theta, \dots, 1.00 \cdot \theta\theta\theta\theta\theta\theta, 1.05 \cdot \theta\theta\theta\theta\theta\theta, \dots, 2 \cdot \theta\theta\theta\theta\theta\theta\theta\theta\theta$ . Hence, the starting penalty is zero and thus reflects the primary endpoint analysis assuming MAR; and the penalty  $1.00 \cdot \theta\theta\theta\theta\theta\theta$  reflects a complete loss of the treatment effect in narsoplimab patients with missing data; and the penalty  $2 \cdot \theta\theta\theta\theta\theta\theta\theta\theta\theta$  reflects a complete reversal of the treatment effect in narsoplimab patients with missing data. For each penalty in the vector  $\{\delta\delta\delta\delta\}$ , missing data in both treatment arms will be imputed as

MAR under placebo and the penalty added to those patients with missing data in the narsoplimab arm. The resulting multiply imputed datasets will be analyzed as per the primary endpoint MMRM model as specified in Section 2.9.2.1 and the results combined using Rubin's rules as described above for Jump to Placebo.

The p-value, treatment effect estimate and 95% CI associated with each penalty will be displayed in a forest plot format to allow identification of the 'tipping point' penalty that renders the primary endpoint analysis p-value non significant.

Example SAS code of the form to perform this second sensitivity analysis is contained in [Appendix 2](#).

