It should be noted that there is no need for a two dimensional tipping point approach whereby penalties are applied to both placebo and narsoplimab as the approach described above, i.e. applying a penalty to the narsoplimab arm alone and zero penalty to the placebo arm, will yield identical results. This is the case since, in both approaches, missing data are multiply imputed under placebo in both arms. The only difference is that when a penalty  $\{\delta\delta\delta\}$  is applied only to narsoplimab patients with missing data and a penalty  $\{0\}$  is applied to the placebo patients with missing data, the net penalty is  $\{\delta\delta\delta\}$ ; whereas if a penalty matrix  $(\{\delta\delta\delta\}, \{\delta\delta\delta\}^{TTT})$  is constructed whereby the penalty vector  $\{\delta\delta\delta\}$  is applied to narsoplimab patients with,

$$\{\delta\delta\delta\} = \{0.00, 0.05, 1.00, 1.05, 2.00\}$$

$$\{\delta\delta\delta\} = \{\delta\delta\delta_0, \delta\delta\delta_{0.05}, \dots, \delta\delta\delta_{1.00}, \delta\delta\delta_{1.05}, \dots, \delta\delta\delta_{2.00}\}$$

and, for each element,  $\delta\delta\delta_{iiii}, jjjj = 0, 0.05, \dots, 2$ , of  $\{\delta\delta\delta\}$ , the same, transposed penalty vector,  $\{\delta\delta\delta\}^{TTT}$ , is applied to placebo patients with missing data, then the net penalty on the estimated treatment effect when applying element  $\delta\delta\delta_{iiii}$  to narsoplimab patients and  $\delta\delta\delta_{kkkk}$  to placebo patients with missing data will simply be  $\delta\delta\delta_{iiii} - \delta\delta\delta_{kkkk}$  which is the same as application of a penalty  $\delta\delta\delta_{iiii-kkkk}$  to narsoplimab patients and a penalty of 0 to placebo patients with missing data.

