## APPENDIX 2. TIPPING POINT MULTIPLE IMPUTATION

A tipping point analysis whereby missing data are imputed in the narsoplimab arm with an increasing degree of penalization and thus find the ‘tipping point’, i.e., that degree of penalization that renders a positive p-value for the primary endpoint non-significant.

All imputation steps are as described in [Appendix 1](#) apart from the second step where monotone missing data are imputed for patients randomized to narsoplimab are adjusted using the **ADJUST** and **SHIFT** options:

```
/*SECONDLY APPYING TIPPING POINT IMPUTATION*/
PROC MI DATA=MI_OUT1 SEED = <SEED> NIMPUTE = 1 OUT=MI_OUT2<DELTA>;
  BY_IMPUTATION_ STRAT1 STRAT2;
  CLASS RANDTRT;
  MONOTONE REG (W36 = BASE W12 W24 / DETAILS);
  MNAR ADJUST(W12 / SHIFT = <DELTA> ADJUSTOBS=(RANDTRT =
  'NARSOPLIMAB')) ;
  MNAR ADJUST(W24 / SHIFT = <DELTA> ADJUSTOBS=(RANDTRT =
  'NARSOPLIMAB')) ;
  MNAR ADJUST(W30 / SHIFT = <DELTA> ADJUSTOBS=(RANDTRT =
  'NARSOPLIMAB')) ;
  MNAR ADJUST(W36 / SHIFT = <DELTA> ADJUSTOBS=(RANDTRT =
  'NARSOPLIMAB')) ;
  VAR W12 W24 W36 BASE RANDTRT;
RUN;
```

The value of the penalty <DELTA> is progressively increased and the code re-run for each increase. This generates a series of **MI\_OUT2<DELTA>** datasets. To each of these datasets, steps 3 to 6 as described in [Appendix 1](#) will be applied, thus giving rise to a multiply imputed treatment effect estimate for each value of <DELTA> for narsoplimab vs placebo, along with its SE and CI. These treatment effect estimates and CIs will be plotted in a stacked forest plot format vs <DELTA>. The first value of <DELTA> whereby the CI includes zero will be identified as the tipping point.

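### The SAP's reason for a narsoplimab-only tipping-point grid is algebraically wrong, and the plan never tests placebo dropouts doing better than imputed

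*SAP*

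**What the plan says.** SAP 2.9.2.2 (Tipping Point Multiple Imputation) sets a grid of penalties from 0 to 2 times the estimated log-scale effect, in steps of 0.05. Missing values are imputed as "MAR under placebo and the penalty added to those patients with missing data in the narsoplimab arm". The top of the grid "reflects a complete reversal of the treatment effect in narsoplimab patients with missing data". Appendix 2 defines the result: the first penalty "whereby the CI includes zero will be identified as the tipping point".

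The SAP then argues that "there is no need for a two dimensional tipping point approach whereby penalties are applied to both placebo and narsoplimab", since "applying a penalty to the narsoplimab arm alone and zero penalty to the placebo arm, will yield identical results". The reason given is: "This is the case since, in both approaches, missing data are multiply imputed under placebo in both arms". It concludes that penalties i on narsoplimab and k on placebo have a net effect of simply i minus k, the same as i − k on narsoplimab alone. No condition on the missing proportions is attached.

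SAP 2.9.2.3 and Protocol 14.1.10.2 apply the same method to both key secondary eGFR endpoints. Neither document gives an expected missing rate.

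**The concern.** A penalty added only to imputed values moves an arm mean in proportion to how many values in that arm are imputed. Using one imputation model for both arms does not make those proportions equal, so the reason offered does not support the identity.

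Two things are at stake. First, the identity is the SAP's only justification for leaving placebo dropouts unpenalised, and so for never asking what happens if they did better than imputed. Second, the stated aim is to find the penalty that removes significance, but the grid stops at a fixed cap with no rule for what to report if significance survives it.

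**Working it through.** **Inputs.** N = 180, 90 per arm (Protocol 14.1.1: "a total N of 180 patients with a baseline UPE ≥ 2 g/day need to be randomized on a 1:1 basis"). SD 0.80 (planning) and 0.63 (blinded estimate), both from SAP 1.3.1. Effect θ = −0.393 as printed there; the 35% reduction it describes is ln(0.65) = −0.431, so both are carried where it matters. Missing proportions pN (narsoplimab) and pP (placebo) are assumptions. Penalties are written as multiples of |θ|, positive meaning worse proteinuria.

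**1. The identity.**
- True shift of the difference: pN·dN − pP·dP.
- SAP's substitute: pN·(dN − dP).
- Gap: (pN − pP)·dP, which is zero only if pN = pP or dP = 0.

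Example: SD 0.80, MAR start, pN = 15%, pP = 5%, penalties (2.0, 2.0).
- Two-dimensional cell: −0.393 + 0.15·0.786 − 0.05·0.786 = −0.314, p = 0.011.
- SAP's supposedly identical cell (0, 0): −0.393, p = 0.001.

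Equal proportions do not rescue the p-values. Shifting a fraction p of an arm by D adds about p(1−p)D²/90 to the variance. In a simulated multiple-imputation check (90 per arm, placebo-based imputation, ANCOVA, Rubin's rules) at 20%/20% missing, cell (2.0, 2.0) and its substitute gave matching estimates (−0.371 and −0.370). Their SEs were 0.130 and 0.120, with p = 0.004 and 0.002.

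**2. Does the error hide a tipping point inside the SAP's own matrix?** That matrix uses the same adverse-direction vector in both arms. An adverse placebo penalty moves the difference by −pP·dP, in favour of narsoplimab. So (dN, 0), which is on the planned grid, has the most adverse estimate for each dN. A closed-form search covered 512 settings: missingness 5–40% in each arm, both effects, both SDs, MAR and placebo-based starts, shift variance included. In none did the matrix tip while the planned grid did not. At 30%/10% in the simulated check, (2.0, 2.0) gave p = 0.063 against 0.001 for its substitute, but the planned cell (2.0, 0) gave p = 0.199, which is harsher.

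**3. The opposite-sign case.** Take pN = 10%, pP = 20%, θ = −0.393 and placebo-based imputation.
- Start: −0.393·(1 − 0.10) = −0.3537.
- Cell (2.0, 0): −0.3537 + 0.10·0.786 = −0.2751.
- Cell (2.0, −1.0), placebo dropouts 1.0·|θ| better: −0.2751 + 0.20·0.393 = −0.1965.

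Base SE = SD·√(2/90): 0.1193 at SD 0.80, 0.0939 at SD 0.63. Added variance for the penalties: 0.09·0.786²/90 = 0.00062 for narsoplimab, and 0.16·0.393²/90 = 0.00027 for placebo where shifted.

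| SD | Cell | Estimate | SE | p |
|---|---|---|---|---|
| 0.80 | (2.0, 0) | −0.275 | 0.122 | 0.024 |
| 0.80 | (2.0, −1.0) | −0.197 | 0.123 | 0.11 |
| 0.63 | (2.0, 0) | −0.275 | 0.097 | 0.005 |
| 0.63 | (2.0, −1.0) | −0.197 | 0.099 | 0.046 |

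The treatment of shift variance matters a little. Two alternatives are to ignore it, or to measure the narsoplimab shift from that arm's observed mean (3·|θ|). They bracket the SD 0.80 values at 0.021–0.028 and 0.099–0.119, and the SD 0.63 values at 0.003–0.007 and 0.036–0.055. The simulated check showed the same pattern: at 10%/30% missing, p went from 0.006 to 0.065; at 10%/10%, from 0.020 to 0.047.

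**4. Reach of the grid.** Ignoring shift variance, the narsoplimab missing proportion needed to tip at 2·|θ| is (1 − 1.96·SE/|θ|)/2 from a MAR start and the same numerator over 3 from a placebo-based start. At θ = −0.431, SD 0.63: (1 − 1.96·0.0939/0.431)/2 = 0.29, or 0.19 over 3. The lowest values come from θ = −0.393, SD 0.80 with shift variance included.

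| Start | Missing proportion below which no tipping point is found |
|---|---|
| Placebo-based | 12% to 19% |
| MAR | 19% to 29% |

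Both starts are shown because the SAP text imputes under placebo yet says of the same grid: "Hence, the starting penalty is zero and thus reflects the primary endpoint analysis assuming MAR". The Appendix 2 code has no placebo-only imputation model.

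**The case against.** A reader might infer that unequal dropout lets the planned grid report no tipping while the rejected two-dimensional analysis would tip. The documents do not support that. The rejected matrix uses same-direction penalties, and step 2 shows that the narsoplimab-only row is its worst case. The opposite-sign gap therefore exists whether or not the identity is true, and asking for it widens the sensitivity analysis rather than restoring something the SAP's matrix contained.

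The cap also has a defence. The SAP gives 2 times the effect a meaning and displays the estimate, CI and p-value for every penalty, so not tipping by the cap is an interpretable statement of robustness up to that bound. Nor is this the only missing-not-at-random check: jump-to-placebo comes first, and Protocol 14.1.10.1 itself describes a narsoplimab-only penalty. Patients who stop drug are asked to complete all visits (Protocol 8.3.1), which may keep missingness low.

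All of this stands and limits the consequence. It does not make the identity true, and it does not cover favourable placebo shifts. Nor does it supply a reporting rule for a search that ends without the promised tipping point.

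**Conclusion.** The identity paragraph is wrong as written, and this needs no assumption about missing rates. Its direct consequence is small, because the planned row is already the most adverse in the matrix it replaces.

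The substantive loss is the untested case of placebo dropouts doing better than imputed. Under the assumed 10%/20% missingness with the printed effect and SD 0.80, that case turns p of about 0.02 into about 0.11. At SD 0.63 the same shift gives about 0.046, which is borderline and not a clear tip. Whether a real result tips depends on missing proportions that the documents do not give.

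The grid may also end without a tipping point when narsoplimab missingness is below roughly 12–19% (placebo-based start) or 19–29% (MAR start). That leaves a reporting rule missing but does not invalidate the analysis. The figures are for the primary endpoint; none was computed for eGFR, where the algebra is the same.

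**What to change.** In SAP 2.9.2.2:
- Delete the paragraph claiming equivalence.
- Run a two-dimensional grid with independent shifts: adverse for narsoplimab, adverse and favourable for placebo.
- Define penalties as multiples of |θ| with a stated direction. The estimate is negative for benefit, so literally adding multiples of it would help narsoplimab.
- Extend each axis until p crosses 0.05 or a stated implausibility bound is reached. Show the p = 0.05 contour and report no tipping up to the bound if it is not crossed.
- State whether zero penalty means MAR or placebo-based imputation, and align Appendix 2.
- Apply the same to both key secondary eGFR endpoints.

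The cost is SAP wording and one further loop in the existing imputation code. The robustness display may look less favourable. The primary test, alpha and sample size do not change.

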## COVID-19

Statistical analysis using the primary analysis method will be performed by excluding the data collected from patients re-initiating study treatment due to the COVID-19 pandemic

The restricted maximum likelihood (REML) method in SAS PROC MIXED will be used to fit the model. The treatment difference in the rate of change in eGFR over 2 years will be estimated from the model along with its standard error, 2-sided confidence interval and p-value. The applicable alpha level will be 5% in a 2-sided test. Denoting time as **T**, the SAS code will be of the form;

```
PROC MIXED DATA=Y COVTEST CL;
  CLASS PATIENT RANDTRT STRAT1 STRAT2;
  MODEL Y = T RANDTRT RANDTRT*T STRAT1 STRAT2 STRAT1*STRAT2/ SOLUTION COVB;
  RANDOM INT T / TYPE=UN PATIENT SOLUTION G GCORR;

  ESTIMATE "INTERCEPT NAR"      INTERCEPT 1 RANDTRT 0 1           / CL ALPHA=0.05;
  ESTIMATE "INTERCEPT PCB"      INTERCEPT 1 RANDTRT 1 0           / CL ALPHA=0.05;
  ESTIMATE "INTERCEPT NAR v PCB" RANDTRT 1 -1 T 0 RANDTRT*T 0 / CL ALPHA=0.05;

  ESTIMATE "SLOPE NAR"          T 1 RANDTRT*T 0 1 / CL ALPHA=0.05;
  ESTIMATE "SLOPE PCB"          T 1 RANDTRT*T 1 0 / CL ALPHA=0.05;
  ESTIMATE "SLOPE NAR v PCB"    T 0 RANDTRT*T 1 -1 / CL ALPHA=0.05;

  ODS OUTPUT "ESTIMATES"=EST;
  ODS OUTPUT SOLUTIONF=F;
  TITLE "RANDOM CO-EFFICIENTS ANALYSIS TOTAL SLOPE EGFR";
RUN;
TITLE;
```

Sensitivity analyses for both key secondary efficacy eGFR endpoints will include:

- Jump to Placebo Multiple Imputation
- Tipping Point Multiple Imputation

- COVID-19

with these analyses executed in the same fashion as described for the primary UPE endpoint.

While prior FDA co-authored publications and supportive simulations demonstrate that the use of fixed weights as per [Cui, Hung and Wang \(1999\)](#) are necessary to avoid alpha inflation associated with the SSRE procedure, an exploratory analysis of eGFR will be performed using an unweighted test statistic for the rate of change in eGFR over 2 years in the high-risk proteinuria group as requested by FDA.

Given the limited eGFR data points during the first 12 weeks of the study, the presence of an early, acute effect on eGFR cannot be meaningfully assessed. Nevertheless, mean change eGFR data will be presented by treatment groups at all sampling timepoints during the 2-year follow-up study period.

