10.2.3.1. Method of Assigning Patients to Treatment Groups

On the day of or up to 24 hours prior to T1, eligible patients will be randomized in the study via the electronic randomization system. Computer-generated permuted block randomization will be created in a ratio of 1:1 double-blind assignment to narsoplimab (active treatment group) or placebo. Randomization will be stratified by the baseline eGFR level (\geq 30 to \leq 45 mL/min/1.73 m² and $>$ 45 mL/min/1.73 m²) and by baseline UPE ($>$ 1 to $<$ 2 g/day and \geq 2 g/day).

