14.1.6.1. Adjustments for Covariates

Efficacy analyses will adjust for randomization strata. Some potential baseline patient and disease characteristics may affect the interpretation of the efficacy results. Subgroup analyses and regression analyses may be performed to adjust for the potential covariate effects. These analyses will be considered exploratory and, if performed, will be discussed in the clinical study report.

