14.1.10.2. Analysis of Rate of Change in eGFR

The analysis of the key secondary efficacy eGFR endpoints (1) the rate of change in eGFR over 2 years in the high-risk proteinuria group and (2) the rate of change in eGFR over 2 years in the all-patients population will be performed only if the primary UPE efficacy endpoint in the high-risk proteinuria group is significant at 5% level of significance in a 2-sided test. If the primary endpoint is significant then key secondary endpoints (1) and (2) will each be sequentially tested at 5% level of significance in a 2-sided test.

The key secondary rate of change in eGFR over 2 years in patients in the high-risk proteinuria group (baseline UPE $\geq 2\text{g/day}$) and in the all-patients population will be analyzed by a random coefficients model for the FAS population. This analysis will be performed after the final database lock.

The random coefficients model is specified as follows:

$$yy_{iiaa} = (\beta\beta_0 + bb_{0ii}) + \beta\beta_1 \cdot GG + (\beta\beta_2 + bb_{2ii})xx_{iiaa} + \beta\beta_3 \cdot GG \cdot xx_{iiaa} + ee_{iiaa}$$

where

- yy_{iiaa} is the eGFR value for patient ii at assessment time jj ;
- xx_{iiaa} is the time of the jj^{th} assessment for patient ii ;
- $GG = 0, 1$ for placebo and narsoplimab
- $\beta\beta_0$ = intercept fixed placebo effect, $\beta\beta_0 + \beta\beta_1$ = intercept fixed narsoplimab effect and $\beta\beta_1$ = the fixed treatment effect on the intercept;
- $\beta\beta_2$ = slope fixed placebo effect, $\beta\beta_2 + \beta\beta_3$ = slope fixed narsoplimab effect and $\beta\beta_3$ = the fixed treatment effect on slope;
- bb_{0ii} and bb_{2ii} are the random intercept and slope effects associated with patient ii ;
- ee_{iiaa} are the residual error for patient ii at time jj , with ee_{iiaa} ;

The random effects, bb_{0ii} and bb_{2ii} are assumed $ii. ii. dd$ Normally distributed with variance components $\sigma\sigma_0^2$ and $\sigma\sigma_2^2$ and, independently, the random error ee_{iiaa} is Normally distributed with variance $\sigma\sigma^2$.

The restricted maximum likelihood (REML) method in SAS PROC MIXED will be used to fit the model. The treatment difference in the rate of change in eGFR over 2 years will be estimated from the model along with its standard error, 2-sided confidence interval and p-value. The applicable alpha level will be 5% in a 2-sided test.

Sensitivity analyses for both key secondary efficacy eGFR endpoints will include:

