$$n = \frac{4(zzzz_{aaaa} + zzzz_{pppp})^2}{(\beta\beta\beta\beta_{DDDD} - \beta\beta\beta\beta_{PPPP})^2} \cdot \frac{\sigma\sigma\sigma_{eeee}^2 + \sigma\sigma\sigma_{bb}^2}{SSSS_{xxxxxxxxxx}}$$

where  $\alpha$  is the 1-sided Type I error,  $\beta$  Type II error,  $zzzz_{aaaa} = \Phi^{-1}(1 - \alpha)$  where  $\Phi^{-1}(\cdot)$  represents the inverse standard Normal distribution function, and  $SSSS_{xxxxxxxxxx}$  is the sum of the squared differences of eGFR measurement times minus the mean time. With eGFR measured 3 monthly over 24 months, then  $SSSS_{xxxxxxxxxx} = 378$ .

Thus, hypothesizing that the 2-year annualized eGFR rate of decline for narsoplimab relative to placebo in the high-risk proteinuria group (baseline UPE  $\geq 2$  g/day) is 3.48 mL/min/1.73 m $^2$ , a sample size of 280 patients (i.e., 140 per treatment group) followed for 2 years post randomization will provide at least 85% power at the 2-sided 5% level to test this hypothesis. Further, the smallest observed improvement in the UPE  $\geq 2$  g/day population that will yield  $p \leq 0.025$  1-sided with  $N = 280$  is 2.3 mL/min/year, in line with [Inker 2021].

Similarly, data from the University of Leicester registry provide an estimate of the annualized eGFR rate of decline in patients with a baseline UPCR of  $> 1$  g/day of  $-4.40$  mL/min/m $^2$  (SE 1.716 mL/min/m $^2$ ), and the between-slope variance component  $\sigma\sigma\sigma_2^2$  was estimated to be 7.8469 $^2$  mL/min/m $^2$  annually ( $= 0.6539^2$  mL/min/m $^2$  monthly) with the residual-error variance  $\sigma\sigma_{ee\varphi_e}^2$  estimated to be  $= 5.9517^2$  mL/min/m $^2$ .

Hypothesizing that the 2-year annualized eGFR rate of decline for narsoplimab relative to placebo in the all-patients population is 2.45 mL/min/1.73 m $^2$ , a sample size of 450 patients

(i.e., 225 per treatment group) followed for 2 years post randomization will provide at least 85% power at the 2-sided 5% level to test this hypothesis. And again, the smallest observed improvement in the overall population that will yield  $p \leq 0.025$  1-sided with  $N = 450$  is 1.6 mL/min/year.

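### The eGFR slope model adjusts for randomisation strata only at the intercept, so the reported SE of the slope difference is slightly too large if strata differ in slope

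*SAP*

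**What the plan says.** Protocol 14.1.6.1 states: "Efficacy analyses will adjust for randomization strata". It does not say whether this means level, slope or both. Protocol 14.1.10.2 says the rate of change in eGFR "will be analyzed by a random coefficients model for the FAS population". The equation printed there, and repeated in SAP 2.9.2.3, has treatment, time, treatment by time and two random effects, but no strata terms.

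The SAS code in SAP 2.9.2.3 does include strata: "MODEL Y = T RANDTRT RANDTRT*T STRAT1 STRAT2 STRAT1*STRAT2/ SOLUTION COVB", with "RANDOM INT T / TYPE=UN PATIENT SOLUTION G GCORR" for the random part. The tested contrast is "T 0 RANDTRT*T 1 -1 / CL ALPHA=0.05", the treatment difference in slope. The two stratification factors and their product are main effects only; none is multiplied by time. Neither document gives a reason.

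On allocation, Protocol 10.2.3.1 says: "Computer-generated permuted block randomization will be created in a ratio of 1:1 double-blind assignment", stratified by baseline eGFR and baseline UPE. SAP 1.3.2 says of each eGFR sample size that it "will provide at least 85% power at the 2-sided 5% level to test this hypothesis".

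**The concern.** A main effect for stratum shifts the eGFR level and leaves one common slope for all strata. The tested quantity is a difference in slopes, so a level shift does not adjust it. If patients at or above 2 g/day decline faster than those below, that difference stays in the random-slope variance, which sets the SE of the tested contrast. The trial balances the arms on these strata by design, but the analysis does not use that balance where the test is made.

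The planned power leaves little slack: both eGFR sample sizes recompute to 85.1% against a target of at least 85%. Even so, what is at stake is about a percentage point of power. The validity of the test is not in question. The text and the code also disagree on whether strata are in the model at all, and that needs settling in any case.

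**Working it through.** **Inputs (SAP 1.3.2 unless noted).** All patients: effect 2.45/year, N = 450, monthly slope variance 0.6539² = 0.4276, residual variance 5.9517² = 35.42. High-risk group: effect 3.48/year, N = 280, monthly slope variance 0.7356² = 0.5411, residual variance 6.5077² = 42.35. Sum of squares of visit times: 378. Registry slopes: -5.44/year (≥ 2 g/day) and -4.40/year (> 1 g/day). High-risk to other mix 60:40 (SAP 2.9.7, stated for the trial and not for the registry).

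**1. Reproduce the plan.** N = 4(z_α + z_β)²/δ² × V, with V = residual variance/378 + slope variance and (1.960 + 1.036)² = 8.98.
- High-risk: V = 0.1120 + 0.5411 = 0.6531, δ = 0.290/month. N = 278.9, so 280; power 85.1%.
- All patients: V = 0.0937 + 0.4276 = 0.5213, δ = 0.2042/month. N = 449.1, so 450; power 85.1%.
- Smallest significant differences are 2.27 and 1.60/year, against the stated 2.3 and 1.6.

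**2. What the intercept terms do.** In simulation (4,000 runs per scenario, variance components taken as known, stratified blocks of four), with complete data on a common schedule, the slope difference and its SE were identical with and without intercept strata terms (differences about 1e-13). With an assumed 15% dropout the all-patients model SE moved from 0.8477 to 0.8468, about 0.1%.

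**3. Size of the stratum effect, all patients.** Assume the registry mix is 60:40.
- Implied slope below 2 g/day: (-4.40 + 0.6 × 5.44)/0.4 = -2.84/year; gap 2.60/year.
- Between-strata variance: 0.6 × 0.4 × 2.60²/144 = 0.0113 per month², which is 0.0113/0.5213 = 2.2% of the per-patient slope variance.
- SE ratio: √(1 - 0.0216) = 0.989, so the model SE falls from 0.8169 to 0.8080/year.
- N for 85% power: 439.4, so 440. Power at 450: 85.8%.

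| Assumed ≥ 2 g/day share | Implied slope < 2 g/day | Share of variance | N | Power at 450 |
|---|---|---|---|---|
| 50% | -3.36 | 1.4% | 444 | 85.6% |
| 60% | -2.84 | 2.2% | 440 | 85.8% |
| 80% | -0.24 | 5.8% | 424 | 87.1% |

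If slopes do not differ by stratum, the gain is zero.

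**4. Is the estimate itself less precise?** No. At the 2.60/year gap the simulated sampling SD was 0.8011 with and without strata-by-time terms, and 0.8145 under simple randomisation with intercept-only strata. Only the reported SE changes. By theory, a test using SE 0.8169 when the sampling SD is 0.8080 has critical value 1.96 × 0.8169/0.8080 = 1.98, a two-sided error of about 4.75%. Its actual power is Φ((2.45 - 1.96 × 0.8169)/0.8080) = 85.3%, so the true gain is nearer half a point. Simulated power was 85.4% and 86.0%; simulated type I error was 4.9% and 5.1%, with Monte Carlo error of about 0.3 points.

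**5. High-risk group.** Every patient is in the upper UPE stratum, so only the eGFR stratum can matter. The documents give no slope by eGFR stratum. Assuming a gap of 0 to 4/year with 20% to 50% of patients in the lower stratum, 0% to 4.3% of the variance lies between strata, N runs from 280 to 268, and power at 280 runs from 85.1% to 86.6%. At a 2/year gap with 30% in the lower stratum the figures are 0.9%, 278 and 85.4%.

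**The case against.** The strongest reply is that this is a modelling choice and breaches no commitment. The protocol promises adjustment for strata without saying it must reach the slope, the SAP code does adjust, and Protocol 14.1.4 says its statistical sections only summarise the SAP. That stands: this is a refinement and not a departure from the protocol. It does not explain why the SAP's own equation and code differ.

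The evidence that slopes differ is also thin. The -4.40 estimate carries a printed SE of 1.716, and the gap to -5.44 is 1.04, about 0.6 of that SE. The two registry groups overlap and their mix is not stated. This stands too, and is why the gain must be given as a range that includes zero.

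The computed gain falls on the last test in the hierarchy, reached only after the UPE test and the high-risk eGFR test succeed. That limits its practical value. The change is also more than one line, because the interim re-estimation and the final two-stage test use the same model. That is a reason to change them together, not a reason to leave them.

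A reader might infer that the slope test gets no benefit from the stratification, or that strata-by-time terms are free precision. The documents do not support either. Stratified 1:1 blocks already balance the strata and reduce the variability of the estimate, and step 4 shows the estimate becomes no more precise when the terms are added. What is missing is credit in the SE.

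**Conclusion.** The point holds as a low-priority refinement. With complete data the strata terms in the slope model do nothing for the tested contrast or its SE. If strata differ in slope, the reported SE is slightly too large and the planned test is valid but mildly conservative.

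At a 60:40 mix the excess in the all-patients SE is about 1.1%, or 0.7 power points on the SAP's formula. This assumes that the registry mix matches the trial's, that the two registry point estimates can be combined despite their overlap and imprecision, and that the SAP's 3-monthly eGFR sampling and complete follow-up apply. For the high-risk test no figure can be derived from the documents; the range in step 5 is assumption only. Nothing here suggests bias or an inflated type I error in the current plan.

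**What to change.** Before the interim unblinding:
- All-patients model: add `STRAT1*T`, `STRAT2*T` and, to match the main-effect product already present, `STRAT1*STRAT2*T`.
- High-risk model: add the eGFR-stratum-by-time term only (`STRAT1*T`, taking `STRAT1` as the eGFR factor). Drop `STRAT2` and `STRAT1*STRAT2`, which are redundant there; the primary UPE code in SAP 2.9.2.1 already uses the eGFR stratum alone.
- Bring the equations in SAP 2.9.2.3 and Protocol 14.1.10.2 into line with the code.
- In SAP 2.9.7, use the same model for the interim conditional-power calculation and for both stage z-values.
- State how the arm-specific slope `ESTIMATE` statements weight the strata. The treatment-by-time contrast itself is unchanged.

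The cost is one degree of freedom in the high-risk model, three in the all-patients model, and minor code changes. No bias or type I error problem appeared in simulation.
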